# STATISTICAL PROCEDURES

Sample size calculations were determined based on a previous meta-analysis investigating the effect of alpha-antagonists in reducing ureteral stent-related discomfort (Lamb et al, BJU Int, 2011). This study included five randomized controlled trials, four of which were placebo controlled. The study found a difference of 8.4 points in the Ureteral Stent Symptom Questionnaire (USSQ) urinary symptom score (mean 20.0, SD 5.6 vs. mean 28.4, SD 6.2) and a difference of 7.2 points in the USSQ pain score (mean 11.9, SD 10.1 vs. mean 19.1, SD 10.9) in the treatment group compared to the control group. Assuming a similar treatment effect, a t-test with a two-sided significance level of 0.05 will require a sample size of 35 patients in each group to detect a difference in the pain score between the two groups with a power of 80%. A sample size of 35 is larger than required to detect a difference in the urinary symptom score with the same power. Assuming a drop-out rate of 10%, 39 patients per group will be randomized.

To compare outcomes, t-tests will be used for continuous variables, and chi-square tests will be used for nominal variables. Statistical analyses will be performed using Stata (Statacorp, College Station, TX, USA). Power and sample size calculation was performed using G\*Power 3.1 (Dusseldorf, Germany).

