# STUDY DESIGN

We propose a prospective, double-blind, randomized, placebo-controlled, single-center trial. 78 patients will be enrolled. All patients will be provided written and informed consent. Eligible participants will be adult patients (aged 18–80 years) who are undergoing unilateral retrograde ureteroscopy with planned ureteral stent placement for treatment of urinary tract stones. The exclusion criteria are as follows: (i) preoperative use of antihistamines, beta-3 agonists, anticholinergics, corticosteroids, and chronic opioid analgesic use; (ii) preoperative indwelling ureteral stent at the time of treatment; (iii) neurogenic bladder, ureteral stricture, interstitial cystitis, or chronic prostatitis; (iv) pregnancy or breastfeeding; (v) planned bilateral ureteroscopy; (vi) solitary or transplanted kidney; (vii) hypersensitivity to antihistamines; (viii) severe renal disease (GFR < 10 ml/min or on dialysis). All patients will provide written, informed consent preoperatively. Unilateral ureteroscopic stone removal surgery will be performed under general anesthesia with a semirigid and/or flexible ureteroscope. At the conclusion of lithotripsy, a silicone double pigtail ureteral stent will be placed. Size and length of the stent will be at the discretion of the treating urologist. Patients will be excluded and will not be randomized if: (i) a ureteral stent

is not deemed necessary; (ii) there is a significant deviation in the operative plan involving a urologic malignancy or tandem stent placement (two stents in one ureter); (iii) a second-stage procedure for further stone treatment is required.

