Following surgery, eligible patients will be randomized into one of two groups in a 1:1 ratio using varying block sizes. The randomization table will be built by a biostatistician and sent directly to the pharmacy who will be responsible for treatment allocation. The patients and the treating urologist will both be blinded to the treatment allocation. Group A will receive fexofenadine 180 mg once daily in addition to standard of care treatment. Group B will receive placebo in addition to standard of care treatment. The study drug will be taken starting on the evening of surgery (post-operative day #0) and will continue until the stent is removed. The routine postoperative standard of care treatment will consist of oral non-steroidal anti-inflammatory agents (NSAIDs). This treatment will be modified as needed on an individualized basis based on contraindications to these medications. If patients require further pain medication, narcotics will be considered on a limited basis depending on individual patient requirement, as per the standard of care, and the amount used will be tracked. Patients will be asked to keep a record of their analgesic usage. Anticholinergic medications may also be prescribed in the postoperative period for patients with significant bother by urinary urgency and frequency. If these medications are prescribed, their usage will also be tracked. Alpha blockers will not be prescribed routinely, but they will be continued in patients who take them chronically. The timing of ureteral stent removal will be determined based on physician and patient preference and will routinely be 1-2 weeks after surgery.

All patients will complete the Ureteral Stent Symptom Questionnaire (USSQ) three times: at their preoperative office visit, at the time of stent removal, and at their follow-up visit after stent removal. At the time of stent removal, patients will also report their usage of NSAIDs, anticholinergics, and narcotics. Patients will also be asked about drug-related adverse effects. The clinical research coordinator will contact patients every 2-3 days to assess for side effects, to maintain compliance to protocol, and to ensure patients are maintaining medication logs.

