The primary outcomes of the study are the USSQ urinary symptom score and pain score. Secondary outcomes include (i) number of office phone calls due to urinary symptoms and pain; (ii) duration of NSAID use; (iii) duration and quantity of narcotic use; (iv) number of emergency department visits; (v) drug-related adverse effects; (vi) other domains of the USSQ.

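### Both primary USSQ scores have a preoperative baseline, but the only analysis named is a t-test without it; prespecify ANCOVA on the matching preoperative score

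*Combined protocol and SAP*

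**What the plan says.** Under Study Design, the questionnaire schedule is: "All patients will complete the Ureteral Stent Symptom Questionnaire (USSQ) three times: at their preoperative office visit, at the time of stent removal", with a third completion at the follow-up visit. The same section places allocation after the operation: "Following surgery, eligible patients will be randomized into one of two groups in a 1:1 ratio using varying block sizes". It also defines the endpoints: "The primary outcomes of the study are the USSQ urinary symptom score and pain score".

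Statistical Procedures bases the sample size on the pain score: "a t-test with a two-sided significance level of 0.05 will require a sample size of 35 patients in each group", for 80% power. The whole analysis plan for outcomes is then one sentence: "To compare outcomes, t-tests will be used for continuous variables, and chi-square tests will be used for nominal variables".

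No regression, covariate or baseline adjustment appears anywhere in the document. It does not say what the preoperative score is for, at which visit the primary scores are compared, or whether the test is on the score itself or on its change from baseline.

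**The concern.** The preoperative USSQ is measured on the same instrument as both primary outcomes, in all patients, before allocation. If it predicts the later score, adjusting for it removes outcome variance that the unadjusted t-test leaves in its standard error. The trial would then collect this information and not use it.

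This matters most for pain, because the design has little slack there: 35 evaluable patients per group give 80.7% power and 34 give 79.5%. The assumed effect is also borrowed from trials of another drug class (alpha-antagonists), and the Background says antihistamines have not been tested for stent symptoms.

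Prespecification is a second, smaller matter. If the groups differ visibly at baseline and no adjustment was planned, any adjustment made afterwards is post hoc.

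**Working it through.** **Inputs from Statistical Procedures.** Pain: difference 7.2, SDs 10.1 and 10.9. Urinary symptoms: difference 8.4, SDs 5.6 and 6.2. Two-sided alpha 0.05; 35 evaluable per group; 10% drop-out; 39 per group randomized.

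**Assumed input.** The correlation ρ between the preoperative score and the outcome score is not in the documents. I take 0 to 0.5.

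**Step 1: reproduce the plan's figure.**

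- Pain: pooled SD = √((10.1² + 10.9²)/2) = 10.51, so d = 7.2/10.51 = 0.685.
- Urinary: pooled SD = √((5.6² + 6.2²)/2) = 5.91, so d = 8.4/5.91 = 1.42.
- Noncentral t with 68 df and noncentrality d·√(35/2): power is 80.7% for pain and over 99.9% for urinary symptoms. At 34 per group pain power is 79.5%, so 35 is the smallest n that reaches 80%.
- Drop-out: 35/0.90 = 38.9, rounded up to 39.

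The stated sample size is correct for an unadjusted t-test on the raw score.

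**Step 2: ANCOVA at the same n.** The residual variance is multiplied by (1 − ρ²), one degree of freedom is lost (67 df), and chance baseline imbalance inflates the variance of the adjusted difference. The noncentrality is d / √[(1 − ρ²)(2/35)(1 + t²/68)], and power is averaged over t following a t distribution with 68 df (normal baseline assumed). The CI half-width is 1.996 × SD × √[(1 − ρ²)(2/35)(1 + 1/66)]. For the t-test it is 1.995 × SD × √(2/35), which gives 5.01 for pain and 2.82 for urinary symptoms.

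| ρ (assumed) | Pain power | Pain CI half-width | Urinary CI half-width |
|---|---|---|---|
| t-test | 80.7% | 5.01 | 2.82 |
| ANCOVA, 0 | 80.1% | 5.05 | 2.84 |
| ANCOVA, 0.1 | 80.5% | 5.03 | 2.83 |
| ANCOVA, 0.2 | 81.6% | 4.95 | 2.78 |
| ANCOVA, 0.3 | 83.6% | 4.82 | 2.71 |
| ANCOVA, 0.4 | 86.4% | 4.63 | 2.60 |
| ANCOVA, 0.5 | 89.9% | 4.37 | 2.46 |

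Simulation of 60,000 trials per value of ρ gave 80.0, 80.4, 81.7, 83.6, 86.4 and 90.1% for pain. Break-even is at ρ of about 0.12; below it ANCOVA loses at most 0.6 points of power.

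**Step 3: chance imbalance.** The SE of the baseline difference is √(2/35) = 0.239 SD, so a gap above 0.25 SD in either direction has probability 0.296. Given a gap of 0.25 SD, the unadjusted pain difference shifts by ρ × 10.51 × 0.25: 0.26 points at ρ = 0.1 and 1.31 at ρ = 0.5, against the assumed 7.2. Over all randomizations this variation is already in the t-test's standard error. It is another view of the loss in Step 2, not an additional one.

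**Step 4: if the t-test is meant for change scores.** With equal variances at the two visits, the variance of the change is 2(1 − ρ) times that of the raw score. At 35 per group, pain power is then 55.8% at ρ = 0.1, 66.6% at 0.3 and 80.7% at 0.5. ANCOVA exceeds this at each of these values.

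**The case against.** The strongest reply is that nothing here is wrong. The test, the effect and the sample size agree with one another, and the plan meets its own power target without a covariate. That stands.

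The benefit also rests on an unknown correlation that may well be low. Study Design excludes patients with a "preoperative indwelling ureteral stent at the time of treatment", so the baseline is taken without a stent in patients awaiting stone treatment, at an office visit whose interval to surgery is not stated. Surgery then treats the stone and adds a stent. At ρ of 0 to 0.2, pain power moves only from 0.6 points below to about 1 point above the t-test. This stands too, and it limits the size of the gain.

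A third objection is that the plan may intend a change-score t-test, which would use the baseline. The raw group means behind the sample size suggest otherwise but do not settle it. That reading does not rescue the plan: ANCOVA is more powerful there as well, and by a wider margin over this range of ρ.

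Fourth, a prespecified unadjusted test is a complete rule, so an observed imbalance does not oblige anyone to adjust. That is fair. Imbalance should not be counted as a separate harm.

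Finally, the plan expects every patient to have a preoperative score, so missing baselines are hypothetical. That is also fair; the rule proposed below is a safeguard.

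**Conclusion.** The concern holds as a recommended improvement in efficiency and prespecification. It is not a validity error: the t-test is unbiased over randomizations and 35 per group is right for it.

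Compared with a t-test on the raw score at 35 per group, ANCOVA changes pain power by −0.6 points at ρ = 0, +2.9 at 0.3 and +9.2 at 0.5. The urinary score gains only precision. The results rest on the plan's effect sizes and SDs, a normally distributed baseline and an assumed range for ρ, so the direction of the trade-off is clearer than its size. The case for acting is the asymmetry: a small, bounded cost against a gain that could be material for the endpoint with the least power in reserve.

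**What to change.** Make ANCOVA the primary analysis of each USSQ score. Suggested wording:

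> Each USSQ score at stent removal will be compared between groups by linear regression on treatment group and the same preoperative USSQ score. The adjusted mean difference and its 95% CI will be reported. A missing preoperative score will be replaced by the mean preoperative score of all randomized patients, calculated without regard to group, so that no patient is dropped for a missing baseline. The unadjusted t-test will be reported as supportive.

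Stent removal is my assumption for the primary time point, because the plan names none; the sponsor must confirm it. The wording also settles the choice between raw and change scores.

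The cost is a few lines of text and one Stata regression command per score, with no new data and no change to the sample size. One degree of freedom is lost, and up to 0.6 points of pain power if ρ is near 0. The missing-baseline rule protects the gain: if, for illustration, a complete-case ANCOVA dropped 2 patients per group (33 left), pain power at ρ = 0.3 would fall from 83.6% to 81.3%.
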